The EURAS study and similar studies (such as INAS-OC¹⁰ and TASC¹¹) have demonstrated that a large, prospective, controlled, long-term cohort study is suitable for (1) safety monitoring of contraceptives, (2) reliable identification of relevant clinical outcomes and (3) providing robust estimates of their incidence. The study described in this protocol has a similar design with a few modifications due to country and product-specific characteristics.

This observational study is being conducted as an imposed obligation for a post-authorization safety study described as a condition for market authorization in accordance with an Article 10a of the EU Regulation 726/2004. This study will include European women using specific contraceptives: FC Patch Low and levonorgestrel-containing oral contraceptives (COC_{LNG})¹². The objective of the study is to assess the cardiovascular and other health risks associated with short and long-term use of FC Patch Low compared with COC_{LNG} during standard clinical practice.

¹⁰ Clinicaltrials.gov identifier: NCT00335257

¹¹ Clinicaltrials.gov identifier: NCT00524771

¹² cf. Section 9.2.1

8 Research question and objectives

The primary objective of the study is to characterize and compare the risks of short (6 months and less)- and long-term use (more than 6 months) of FC Patch Low with COC_{LNG}, in a study population that is representative for the actual users of the individual preparations. This includes an estimate of the absolute risk of rare serious adverse outcomes.

The main clinical outcomes of interest for the short and long-term follow-up are venous thromboembolism (VTE), specifically:

- Deep Venous Thrombosis (DVT) of the lower extremities (ICD-10 codes: I80.1, I80.2); excluding I80.3
- Pulmonary Embolism (PE); this includes the ICD-10 codes I26.0 and I26.9

Furthermore, sensitivity analyses are planned in order to

- 1) evaluate the impact of including I80.3 (phlebitis and thrombophlebitis of lower extremities, unspecified), which means that DVT of the lower extremities plus I80.3 plus pulmonary embolisms are analyzed
- 2) all DVTs and pulmonary embolisms.

Secondary objectives of the study are to measure/describe for FC Patch Low users and compare to users of COC_{LNG} during standard clinical practice;

- All VTE, including thromboses of renal, mesenteric, portal and retinal veins¹³

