9.2.2 Selection of Study Population

Approximately 50,500 FC Patch Low users and 50,500 users of COC_{LNG} (including adolescents) will be recruited by participating physicians. Overall, 101,000 study participants are needed in order to provide approximately 150,000 woman-years (WY) (cf. Section 9.5), assuming a drop-out rate of approximately 0.7% per month.

Recruitment of study participants will be conducted via existing networks of contraceptive-prescribing health care professionals (e.g. gynecologists and general practitioners) who have participated in similar cohort studies in the past. Physicians will recruit FC Patch Low and

COC_{LNG} users in a 1 to 1 ratio. It is expected that this ratio reflects approximately the ratio of starter and restarter prescriptions of FC Patch Low and COC_{LNG} under routine clinical conditions. Only after the decision of the contraceptive prescription has taken place, the physician may ask the woman for study participation. For every FC Patch Low user recruited, the physician has to recruit the next new COC_{LNG} user (starter or restarter) who is willing to participate in the study.

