Subjects will be considered for enrollment in this study after the participating physician has determined that FC Patch Low or COC_{LNG} use is appropriate. There will be no specific medical inclusion/exclusion criteria and no age restrictions. However, women who 1) have been pregnant within 3 months before treatment initiation or 2) have a history of cancer/chemotherapy or an increased genetic risk for VTE at baseline will be excluded from the analysis of VTE. All women who are eligible are to be asked by their physician if they are willing to participate. As this is a non-interventional study, the possibility to participate in the study should not be discussed with the study participant before both - physician and study participant - agree upon the prescription. The physician is to explain the nature of the study, its purpose and associated procedures, and the expected duration of follow-up for each woman prior to her entry into the study. Each woman is to have ample opportunity to ask questions and must be informed about her right to withdraw from the study at any time without disadvantage and without having to provide reasons for her decision. This information will be provided on an informed consent and data privacy form, which must be signed by all study participants. This study has no age restrictions and adolescents can be asked for participation in countries where no ethical or regulatory restrictions for that age group exist. As adolescents are a specifically protected group, local law might require a parent's or guardian's signature, which will then additionally to that of the adolescent study participant be provided on the informed consent form. All documents are to be approved by the relevant local Ethics Committees and the relevant Data Privacy Office, if applicable.

Once enrolled, a study participant may discontinue (and restart) use of hormonal contraception or may switch to another hormonal contraceptive at any time. However, subjects will continue to be followed whether or not they remain on the prescribed contraceptive, provided that they do not withdraw their consent. For the primary analysis outcomes of interest/adverse events will be assigned to the treatment at the time the outcome/event occurred. During the follow-up phase, subjects will be asked whether they have discontinued contraceptive use. Information on the date and reason for discontinuation during the follow-up phase will also be collected.

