9.5 Study size

The sample size considerations are based on the expected VTE incidence for COC_{LNG} of 10 VTE per 10,000 WY²⁰, which was agreed upon recently with CHMP in a comparable PASS that is conducted by ZEG. It is expected that FC Patch Low is associated with a VTE risk that is not higher than the risk associated with COC_{LNG}.

The study should be powered to test non-inferiority of FC Patch Low treatment regarding VTE risk in comparison to COC_{LNG} use. Sample size calculations for a non-inferiority test of two exponential survival curves [6;7] showed that an expected number of 150 VTE cases should be sufficient to reach this goal. These calculations are based on the following assumptions: 1) one-sided α of 0.05; 2) power (1- β) of 0.80 and 3) non-inferiority limit on hazard ratio of 1.5.

At an incidence rate of 10.0/10,000 WY a total of 150 VTE cases could be expected within 150,000 WY. The drop-out rate in similar studies has been approximately 0.7% per month. Assuming 1) a recruitment phase of 60 months, 2) a follow-up phase of 12 - 24 months, and 3) a loss to follow-up rate of about 5%, follow-up of 101,000 study participants (50,500 FC Patch Low users and 50,500 COC_{LNG} users) for up to 24 months would result in approximately 150,000 WY (see table 1).

Based on these scenarios, the study is sufficiently powered to exclude a 1.5-fold VTE risk for FC Patch Low users compared to COC_{LNG} users in the event that the true VTE risk among FC Patch Low users is not higher than among COC_{LNG} users.

However, precise power calculations based on actual incidences and drop-out rates should be done on the basis of follow-up data 1) before the end of the recruitment phase and 2) after availability of 30,000 WY of observation. If these calculations do not confirm the assumed incidence and drop-out rates the Safety Monitoring and Advisory Council will discuss the need to decrease or increase the number of study participants and/or follow-up times.

The sample size needed for the investigation of the VTE risk is also sufficient for the evaluation of secondary outcomes – except ATE. Acute myocardial infarction and stroke are very rare in a female population of reproductive age. This study is powered to exclude a 2.5-fold risk of ATE. This is sufficient to screen for safety signals and substantial effects.

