To monitor the incidence rate and recalculate the study size, if necessary, the incidence rate observed in this study will be provided with each interim report.

²⁰ 'idiopathic' pulmonary embolism and deep venous thrombosis of the lower extremities

Table 1: Expected observation time²¹

Time after study start [month]	Sub-cohorts recruited during month						
	1	2	...	24	25	...	60
	Average number of women in follow-up						
1	1,677						
2	1,665	1,677					
...				
24	1,427	1,437	...	1,677			
25		1,427	...		1,677		
...			
60						...	1,677
...					
71							1,563
72							1,552
WY	3,097	3,076	...	2,635	2,617	...	1,059
Total WY (crude)	170,023						
Total WY (corrected for loss to follow-up and 'within study switchers' who do not contribute to exposure of starter and restarter)	~151,000						

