This study combines several methodological strengths that are substantial for the validity of the results: i) prospective, comparative cohort design; ii) availability of important confounder information (e.g., BMI and family history of VTE); iii) validation of outcomes of interest and the exposure of the relevant cases; iv) comprehensive follow-up procedure and very low loss to follow-up to minimize underreporting; v) independent, blinded adjudication of VTE cases; vi) relevant statistical analyses (e.g., stratified analyses by user status and exposure period; comparison of isochronous, new user cohorts; sensitivity analyses on the impact of the adjudication process, outcome definition, and prognostic factor/covariate selection); vii) study population representative for oral contraceptive users under routine clinical conditions; viii) generalizability of results as hormonal contraceptive use in this study reflects routine clinical use and study participation is not limited by medical inclusion and exclusion criteria; ix) supervision by an independent Safety Monitoring and Advisory Council, and scientific independence from the study funder.

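### The absolute VTE rate would come from a population with higher-risk women removed, while the objective promises the rate in actual users; the effect on power is small and not established

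*Protocol*

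**What the plan says.** Section 9.2.2 of the protocol enrols any new user of either product, with no medical criteria and no age limit. It then names three groups who are enrolled and followed but "will be excluded from the analysis of VTE": women pregnant in the 3 months before treatment starts, women with a history of cancer or chemotherapy, and women with an increased genetic risk of VTE at baseline. The restriction is not confined to the hazard ratio or to one model.

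The primary objective in section 8 is to characterize and compare risks "in a study population that is representative for the actual users of the individual preparations", and it expressly includes the absolute risk of rare serious outcomes. VTE is the main outcome of interest. Section 9.9 lists generalizability among the strengths, partly because "study participation is not limited by medical inclusion and exclusion criteria".

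On study size, section 9.2.2 says: "Overall, 101,000 study participants are needed in order to provide approximately 150,000 woman-years (WY)". Section 9.5 translates this into 150 expected VTE at 10 per 10,000 woman-years. Besides monthly drop-out of 0.7%, Table 1 makes one further deduction, of 11%. Its total is described as "corrected for loss to follow-up and 'within study switchers' who do not contribute to exposure of starter and restarter". The women excluded from the VTE analysis appear in no deduction. A footnote in section 9.5 says that the planning rate of 10 per 10,000 is for 'idiopathic' pulmonary embolism and lower-extremity DVT.

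**The concern.** An absolute rate is only as good as the match between its denominator and the population it is said to describe. The excluded groups are not a random subset. Section 9.3.2 itself counts pregnancy, delivery and chemotherapy among acute VTE risk factors, and raised genetic VTE risk is a risk factor by definition. Removing these women would be expected to lower the rate. A regulator or prescriber who reads the result as the rate in actual users, as section 8 invites, would then see too low a figure for both cohorts. Restricting the hazard ratio can be defended as a way to limit confounding. That reasoning does not carry over to the absolute rate.

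The secondary issue is bookkeeping. Excluded women contribute no woman-years to the primary analysis, yet the 150,000 woman-years are built from everyone enrolled.

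**Working it through.** **1. Which VTE analysis could give the promised rate?** Section 8 asks for absolute risk in a population representative of actual users. Section 9.2.2 takes the three groups out of the VTE analysis as a whole. Section 9.7 plans incidence rates, excess risks and hazard ratios, and names no VTE incidence in all enrolled women. So the protocol specifies no analysis that delivers the all-user VTE rate. This step needs no numbers.

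**2. Size of the gap in the absolute rate.** Let s be the share of woman-years excluded and k the ratio of the VTE rate in excluded women to that in analysed women. The documents give neither, so both are assumed. With an analysed rate of 10 per 10,000 woman-years:

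all-user rate = 10 × (1 − s + s·k)

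- s = 2%, k = 3: 10 × (0.98 + 0.06) = 10.4
- s = 5%, k = 3: 10 × (0.95 + 0.15) = 11.0
- s = 5%, k = 5: 10 × (0.95 + 0.25) = 12.0
- k = 1: 10.0 for any s, so no gap

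**3. Reproducing the event target.** Section 9.5 gives "one-sided α of 0.05", "power (1- β) of 0.80" and "non-inferiority limit on hazard ratio of 1.5". The true hazard ratio is taken as 1 and recruitment is 1:1.

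Events = 4 × ((1.645 + 0.842) / ln 1.5)² = 4 × (2.487 / 0.4055)² ≈ 150.4

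This agrees with the stated 150. At 10 per 10,000, 150,000 woman-years give 150 events. Power at 150 events is Φ(√(150/4) × 0.4055 − 1.645) = Φ(0.838) = 79.9%.

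**4. Power after exclusion.** With E = 150 × (1 − s), s assumed, and power = Φ(√(E/4) × ln 1.5 − 1.645):

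| s | Events | Power |
|---|---|---|
| 0 | 150.0 | 79.9% |
| 1% | 148.5 | 79.6% |
| 2% | 147.0 | 79.2% |
| 5% | 142.5 | 78.1% |
| 10% | 135.0 | 76.1% |

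Up to s = 5% the loss is under 2 points.

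**5. How much slack is there?** Table 1 prints 170,023 crude woman-years; 170,023 × 0.89 = 151,320, shown as about 151,000. I rebuilt the total from 1,683 women per month, 0.7% monthly drop-out and the 11% deduction.

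- If women enrolled in the last year are followed to the end of the study, as section 9.2 describes, the crude total is about 176,300 to 177,800. Corrected, it is about 157,000 to 158,000. Power is then about 81% at s = 2% and about 80% at s = 5%.
- If women in the last 12 monthly cohorts are each cut off at 12 months, the crude total is about 168,100 and the corrected total about 149,600. There is then no slack at all.

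The margin above 150,000 therefore depends on which follow-up rule is used.

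**The case against.** The best defence is that the three statements can all be true together. Participation is indeed unrestricted, the enrolled population may well be representative, and only one analysis is restricted, openly. That stands as far as the wording goes: there is no literal contradiction between sections 8, 9.2.2 and 9.9. It does not supply the missing rate, because VTE is the main outcome and section 9.2.2 restricts its whole analysis.

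A second defence is that tables and analysis details belong in the statistical analysis plan, as section 9.7 says. This would carry weight if the protocol had left the VTE population open. It fixed it instead, so an analysis plan that followed the protocol would reproduce the mismatch.

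On power, a reader might infer that any realistic exclusion takes the study below 80%, or that the stated power refers to a different population. The documents support neither.

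- The excluded share is not given, and the slack depends on the follow-up rule (step 5).
- The power rests on 150 events, which reproduces.
- The planning rate is for 'idiopathic' VTE, which section 9.3.2 defines by dropping cases with acute risk factors such as pregnancy, delivery and chemotherapy. The input therefore already overlaps in part with the exclusions. The overlap is incomplete, because that definition removes cases whereas section 9.2.2 removes women with all their woman-years.
- The primary endpoint is not limited to idiopathic cases, which would add events.
- Section 9.5 plans power recalculation before recruitment ends and after 30,000 woman-years, with the option of changing numbers or follow-up. It does not say that the recalculation uses the VTE analysis set.

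Pregnancy may be a reason for the two-month break that defines a restarter, but that is conjecture and gives no share.

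**Conclusion.** The point holds for the absolute rate. As written, the plan reports a VTE incidence for a selected population under an objective that promises the incidence in actual users. That the rate would tend to be too low rests on the excluded women having a higher VTE rate than the rest, which the protocol's own list of risk factors makes plausible. The size is unknown: 10.4 to 12.0 against 10 per 10,000 woman-years in the illustrations, all on assumed shares and rate ratios.

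For study size, only a minor point remains. No deduction is made for the excluded women, and the text does not say which population the woman-years and the planning rate describe. For an assumed 1% to 5% exclusion, power is 79.6% to 78.1%, starting from 79.9%. This cannot be called a definite shortfall.

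**What to change.** In section 9.7, keep the exclusions for the hazard ratio and add the absolute VTE incidence per cohort in all enrolled starters and restarters, next to the restricted rate. In section 9.9, limit the generalizability statement for VTE to the all-enrolled rate.

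In section 9.5 and Table 1, state that the woman-years, the expected events and the power re-check at 30,000 woman-years refer to the VTE analysis set, with the expected or observed excluded share shown. Say which population and which outcome the 10 per 10,000 rate covers, given that it is footnoted as 'idiopathic' and the primary endpoint is not.

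The cost is one extra incidence table from data already being collected, since the excluded women are enrolled and followed, plus wording changes. No additional participants are needed for this.

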9.2.3 Baseline Survey

Each physician's office will be provided with simple questionnaires for collecting data at baseline. The baseline visit will take place at the participating physician's office. Only after FC Patch Low or a COC_{LNG} has been prescribed will the physician discuss the study with the subject. This ensures that participation in the study is not considered a requirement for treatment. All women who received a new FC Patch Low or COC_{LNG} prescription are to be

asked to participate. After discussing the study details (including content and duration of follow-up contacts, use of data collected, etc.), each subject will be asked to provide written informed consent to participate in the study. If the subject needs time to consider participation, she will be free to leave the physician's office with her prescription and take an appropriate period to decide whether to participate. She can complete the baseline questionnaire and informed consent at home, and multiple ways will be offered to return the documents.

The informed consent will include permission for study data to be collected and analyzed and for contacts to be made by the ZEG study team at intervals during the follow-up phase for collection of study information. Each subject will also be asked to provide information regarding alternative contacts (a close relative or friend, or primary care physician) if ZEG cannot reach the subject after several attempts. Permission for ZEG to contact a subject's primary care physician/attending physician(s) and to review applicable national health databases (where possible and permissible) for relevant subject information will also be sought. Follow-up frequency by ZEG will be explained, and the content of follow-up contacts will be described.

Confidentiality will be maintained throughout the study and no personal information will be shared with alternative contacts. The funder will not have access to names, addresses, or alternative contact information for the subjects and all individual subject data will remain anonymous. Personal and medical information will be recorded on separate documents. ZEG will ensure that access to personal information is restricted in accordance with data privacy rules.

The following information will be recorded at the baseline visit after the study participant has provided written informed consent: prescribed hormonal contraceptive, user status (starter/restarter), risk factors (e.g. personal and family history of VTE and ATE, age, BMI), demographic and medical history, including medication history, history and duration of use of hormonal contraceptives and previous participation in studies (e.g. clinical or observational studies). Additionally, information will be collected on the receipt of the patient information card (study participants will be asked at baseline and follow-up) and the checklist for prescribers (physicians will be asked at baseline). Study participants will also give their contact details like addresses, e-mail addresses and phone numbers, those of their relatives or friends, and the primary care physician. Names, addresses and phone numbers are to be documented on a separate sheet, in compliance with data protection regulations.

9.2.4 Follow-Up Phase

ZEG will perform all follow-up activities during this phase of the study. All subjects who provide written informed consent will be contacted for follow-up regardless of the duration of treatment or whether they discontinue treatment. Subjects who withdraw their consent for follow-up will not be contacted. The funder will not have access to names, addresses, or alternative contact information for the subjects.

Follow-up questionnaires will be mailed to the study participants at 6, 12 and 24¹⁸ months after study entry to collect information regarding major safety outcomes.

The specific safety data to be collected during follow-up will focus on VTE (in particular deep venous thrombosis of the lower extremities and pulmonary embolism), arterial thromboembolism (in particular AMI and stroke), the outcomes reflecting the other secondary objectives as well as all other serious adverse events,¹⁹ including cancer and specifically gynecological cancers. Subjects who report any of these outcomes will be asked to provide their primary care physician's/treating physician's name and address information. ZEG will contact the relevant physician (the attending physician is in most cases not the recruiting physician) and inform him/her about the study objectives and will share the subject's informed consent to access her medical information. Follow up by ZEG will include obtaining hospital records and/or discharge summaries, medical history, treatment dates, and concomitant medication use. A qualified medical expert (i.e., pharmacovigilance physician) on the ZEG study team will assess the likelihood of a causal relationship to study treatment for each serious or unexpected adverse drug reaction in accordance with a predefined algorithm (cf. Section 9.10.3).

At each follow-up contact, subjects will be asked about the exact details and timing of their oral contraceptive use, and whether they continue to use the prescribed study medication.

